4.1 Efficacy Endpoints

The primary efficacy endpoint is the same as described in the M-SAP.

The following secondary efficacy endpoints are adjusted for multiplicity and will be evaluated hierarchically:

- Time to first decline of 2 points or greater post baseline in the ALSFRS-R total score among participants in the FAS with bulbar dysfunction at baseline defined as an ALSFRS-R bulbar domain (Q1-Q3) score of less than 12,

- Proportion of participants experiencing no worsening in the ALSFRS-R bulbar domain (Q1-Q3) score from baseline through Week 24 among all participants in FAS,
- Rate of change in respiratory function as measured by slow vital capacity (SVC) maximum percent predicted from baseline through Week 24 among participants in FAS with bulbar dysfunction at baseline defined as an ALSFRS-R bulbar domain (Q1-Q3) score of less than 12,
- Time to first decline of 1-point or greater post baseline in the ALSFRS-R bulbar domain (Q1-Q3) score among all participants in FAS,
- Time to death or death equivalent through Week 24 among all participants in FAS.

Other Secondary Efficacy Endpoints (pre-specified non multiplicity adjusted non-hierarchical)

- Time to first decline of 2 points or greater post baseline in the ALSFRS-R total score among participants in FAS,
- Proportion of participants experiencing 5 points or less decline in the ALSFRS-R total score from baseline through Week 24 among all participants in FAS,
- Proportion of participants experiencing 5 points or less decline in the ALSFRS-R total score from baseline through Week 24 among all participants in FAS with baseline ALSFRS-R greater than or equal to 36 (Early in disease),
- Proportion of participants experiencing 5 points or less decline in the ALSFRS-R total score from baseline through Week 24 among all participants in FAS with bulbar dysfunction at baseline defined as an ALSFRS-R bulbar domain (Q1-Q3) score of less than 12,
- Rate of change in ALSFRS-R Total Score from baseline through Week 24 among participants in FAS with bulbar dysfunction at baseline defined as an ALSFRS-R bulbar domain (Q1-Q3) score of less than 12,
- Proportion of participants experiencing no or only a 1-point decline in the ALSFRS-R bulbar domain (Q1-Q3) score from baseline through Week 24 among participants in FAS with bulbar dysfunction at baseline defined as an ALSFRS-R bulbar domain (Q1-Q3) score of less than 12,

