- Time to first decline of 1 or more points post baseline in the ALSFRS-R bulbar domain (Q1-Q3) score among participants in FAS with bulbar dysfunction at baseline defined as an ALSFRS-R bulbar domain (Q1-Q3) score of less than 12,
- Proportion of participants experiencing no worsening in the ALSFRS-R bulbar domain (Q1-Q3) score from baseline through Week 24 among all participants in FAS with delta-FRS slower than -0.75 points/month (slow progressors),
- Proportion of participants with ALSFRS-R bulbar domain (Q1-Q3) score greater than or equal to 9 (out of 12) at Week 24 among all participants in FAS with bulbar dysfunction at baseline defined as an ALSFRS-R bulbar domain (Q1-Q3) score of less than 12,

- Proportion of participants experiencing no worsening in the ALSFRS-R bulbar domain (Q1-Q3) score from baseline through Week 24 among all participants in FAS with baseline ALSFRS-R greater than or equal to 36 (Early in disease),
- Rate of change in CNS-BFS total score from baseline through Week 24 among all participants in FAS,
- Rate of change in CNS-BFS total score from baseline through Week 24 among participants in FAS with bulbar dysfunction at baseline defined as an ALSFRS-R bulbar domain (Q1-Q3) score of less than 12,
- Change in HHD upper extremity percentage from baseline through Week 24,
- Change in HHD lower extremity percentage from baseline through Week 24,
- Change in log transformed serum NfL from baseline through Week 24 among all participants in FAS,
- Change in log transformed serum NfL from baseline through Week 24 among participants in FAS with bulbar dysfunction at baseline defined as an ALSFRS-R bulbar domain (Q1-Q3) score of less than 12,
- Change in log transformed serum NfL from baseline through Week 24 among participants in FAS by NfL median baseline split (slow vs fast progressors),
- Rate of change in ALSFRS-R total score from baseline through Week 24 among participants in FAS who were not on Nuedexta at baseline,
- Rate of change in ALSFRS-R total score from baseline through Week 24 among participants in FAS who were not on Nuedexta at baseline and with bulbar dysfunction at baseline defined as an ALSFRS-R bulbar domain (Q1-Q3) score of less than 12,
- Rate of change in CNS-BFS total score from baseline through Week 24 among participants in FAS who were not on Nuedexta at baseline,

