- Rate of change in CNS-BFS total score from baseline through Week 24 among participants in FAS who were not on Nuedexta at baseline and with bulbar dysfunction at baseline defined as an ALSFRS-R bulbar domain (Q1-Q3) score of less than 12,
- Proportion of participants experiencing no worsening in the CNS-BFS total score from baseline through Week 24 among all participants in FAS who were not on Nuedexta at baseline,
- Time to first increase of 5 points or more post baseline in the CNS-BFS total score among all participants in FAS who were not on Nuedexta at baseline, and
- Rate of change in ALSFRS-R total score from baseline through Week 24 among participants in FAS who were on Nuedexta at baseline.

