4.2 Exploratory Endpoints

The following categories of exploratory endpoints will be evaluated:

- Rate of change in ALSFRS-R bulbar domain (Q1-Q3) score from baseline through Week 24 among participants in FAS,

- Rate of change in ALSFRS-R bulbar domain (Q1-Q3) score from baseline through Week 24 among participants in FAS with bulbar dysfunction at baseline defined as an ALSFRS-R bulbar domain (Q1-Q3) score of less than 12,
- Proportion of participants experiencing no worsening in the ALSFRS-R bulbar domain (Q1-Q3) score from baseline through Week 24 among all participants in FAS with delta-FRS less than -0.75 points/month (fast progressors),
- Rate of change in ALSFRS-R bulbar domain (Q1-Q3) score from baseline through Week 24 among all participants in FAS with delta-FRS greater than -0.75 points/month (slow progressors),
- Time to first decline of 1 or more points post baseline in the ALSFRS-R bulbar domain (Q1-Q3) score among participants in FAS with no bulbar dysfunction at baseline defined as an ALSFRS-R bulbar domain (Q1-Q3) score of 12,
- Change in other ALSFRS-R domain scores (fine motor, gross motor, respiratory, and fine and gross motor combined),
- Change in strength: HHD global percentage, HHD0, and HHD0²,
- Change in quantitative voice characteristics as measured by Aural Analytics: maximum phonation time, pause rate, breathy vocal quality, pitch instability, regulation of voicing, articulatory precision, speaking rate, articulation rate, and monotonicity,
- Change in biofluid biomarkers of neurodegeneration and neuromuscular degeneration: serum creatinine, and serum and cerebrospinal fluid (CSF) neurofilament light chain (NfL),
- Change in patient-reported outcomes: ALSAQ-40 physical mobility, independence in activities of daily living, eating and drinking, communications, and emotional reactions domain scores and ALSAQ-40 symptom index, CNS-BFS total score, and CNS Lability Scale (CNS-LS),
- Change in plasma concentration of pridopidine and its metabolites,
- Change in respiratory function as assessed by home spirometry, and

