6.5 Secondary Efficacy Analyses

6.5.1 Hierarchical Testing

Primary inference for secondary efficacy endpoints will be based on analysis of the FAS analysis set or subsets of the FAS analysis set as defined below. Primary estimates and inference for time-to-event endpoints will be by Kaplan-Meier product-limit estimates and log-rank test (see Section 6.5.6 below). Primary estimates and inference for responder endpoints will be by logistic regression as described in Section 6.5.5 with missing data handled as indicated in Section 3.6. Primary estimates and inference for rate of change of continuous endpoints will be by a random-slopes linear mixed model (see Section 6.5.3 below). The sequence for testing secondary efficacy endpoints is the following:

1. Time to first decline of 2 points or greater post-baseline in the ALSFRS-R total score among participants in FAS with bulbar dysfunction at baseline defined as an ALSFRS-R bulbar domain (Q1-Q3) score of less than 12,

2. Proportion of participants experiencing no worsening in the ALSFRS-R bulbar domain (Q1-Q3) score from baseline through Week 24 among all participants in FAS,
3. Rate of change in respiratory function as measured by slow vital capacity (SVC) maximum percent predicted from baseline through Week 24 among participants in FAS with bulbar dysfunction at baseline defined as an ALSFRS-R bulbar domain (Q1-Q3) score of less than 12,
4. Time to first decline post baseline of 1 point or greater in the ALSFRS-R bulbar domain (Q1-Q3) score among all participants in FAS, and
5. Time to death or death equivalent through Week 24 among all participants in FAS.

If the primary analysis indicates a significant slowing in disease progression from the Bayesian shared-parameter, repeated-measures model of ALSFRS-R and mortality, then each secondary efficacy endpoint in succession would be declared significant in the specified sequence using a comparison-wise criterion of two-tailed $p < 0.05$. After the first failure to declare significance, no endpoints lower in the hierarchy can be significant. This sequential closed-testing procedure controls the overall type 1 error rate at 5%. Nominal comparison-wise p-values for secondary efficacy endpoints will also be reported.

All secondary efficacy analyses specified here for hierarchical testing will also be analyzed in the mITT analysis set as sensitivity analyses.

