6.5.12 Subgroup Analyses

In addition to the subgroups specified in the M-SAP, the following additional subgroups will be analyzed in the random-slope model (see Section 6.5.3) for ALSFRS-R total score and SVC in the FAS analysis set:

- Baseline use of riluzole and edaravone (neither, riluzole only, edaravone only, both),
- Age (less than 65 years vs. 65 years or older),
- Sex (female vs. male),
- Race (white vs. any minority race with greater than 5% prevalence in the sample),
- Ethnicity (Hispanic or Latino vs. non-Hispanic or Latino),
- Weight (less than 43 kg, 43 to less than 56 kg, 56 to less than 77 kg, 77 to less than 150 kg, 150 kg or more),

- BMI (less than 18.5 kg/m², 18.5 to less than 25 kg/m², 25 to less than 30 kg/m², 30 to less than 40 kg/m², 40 kg/m² or more),
- Chronic kidney disease (CKD) stage (stage 1 or better [eGFR 90 mL/min/1.73m² or more], stage 2 [eGFR 60 to 89 mL/min/1.73m²], stage 3 [eGFR 30 to 59 mL/min/1.73m²], stage 4 [eGFR 15 to 29 mL/min/1.73m²], stage 5 [eGFR less than 15 mL/min/1.73m²]),
- Time since onset of weakness (less than 18 months vs. 18 months or longer),
- El Escorial and time since onset of weakness (El Escorial definite and less than 18 months vs. not both),
- Baseline symptom severity (all ALSFRS-R questions scored 2 or greater vs. any question scored 0 or 1),
- Early disease state (all ALSFRS-R questions scored 2 or greater, SVC 80%-predicted or greater, and time since symptom onset less than 24 months vs. not meeting all three criteria),
- Baseline serum urate concentration (less than 5.5 mg/dL vs. 5.5 mg/dL or greater),
- Baseline plasma NfL concentration (by median split), and
- Site (individual sites with at least 5 participants per treatment group and all participants from sites with fewer than 5 participants per treatment group pooled).

For each classification, unknown, not reported, and missing will be considered one group. All individuals not included in a specified subgroup will be combined into a mixed, "other" group. The "other" group will be included in analyses if its prevalence is greater than 5%; otherwise, the "other" group will be excluded.

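### Eighteen of the 24 non-hierarchical secondary endpoints are subgroup-based and the R-SAP names no treatment-by-subgroup comparison, so a one-stratum result is open to over-reading

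*SAP*

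**What the plan says.** SAP section 4.1 separates five hierarchical secondary endpoints from a second list headed "Other Secondary Efficacy Endpoints (pre-specified non multiplicity adjusted non-hierarchical". That second list has 24 entries, many of them defined inside one baseline stratum:

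- **Nuedexta.** One entry is "Rate of change in ALSFRS-R total score from baseline through Week 24 among participants in FAS who were not on Nuedexta at baseline". Another is "Rate of change in ALSFRS-R total score from baseline through Week 24 among participants in FAS who were on Nuedexta at baseline". The CNS-BFS entries defined by Nuedexta use are all in non-users.
- **Delta-FRS class.** The no-worsening responder endpoint on the bulbar domain is listed as secondary "among all participants in FAS with delta-FRS slower than -0.75 points/month (slow progressors", while section 4.2 lists it as exploratory "among all participants in FAS with delta-FRS less than -0.75 points/month (fast progressors".
- **Baseline ALSFRS-R of 36 or more.** Two responder endpoints use this cut-off. Neither has a counterpart below 36.

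Section 6.5.3 gives the random-slopes model. Nuedexta enters as a covariate and as covariate by month; there is no treatment by Nuedexta by month term. The section reports 95% bounds and reads a significant slope difference favouring active as support for benefit. Section 6.5.1 says nominal p-values for secondary endpoints will be reported.

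Section 6.5.12 says that, beyond those in the Master SAP, "the following additional subgroups will be analyzed in the random-slope model" for ALSFRS-R total score and SVC. Its list does not include Nuedexta, delta-FRS class, baseline bulbar dysfunction or the cut-off of 36, and it names no interaction test.

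**The concern.** A p-value inside one stratum answers whether there is an effect in that stratum. It does not answer whether the effect differs from that in the other stratum. Where one stratum is reported alone, or two are tested separately, a small p-value in one invites the reading that the drug works there and not elsewhere. Chance can produce that pattern, and so can unequal stratum sizes when the effect is uniform.

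The layout adds to the risk because the strata are not treated symmetrically. For CNS-BFS only Nuedexta non-users are shown, slow and fast progressors sit in different tiers, and the 36-point subgroup has nothing beside it. At stake is how a nominal subgroup result is described in the study report, particularly if the whole-population result is weak.

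**Working it through.** **Count of the second list in SAP section 4.1**

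| Population | Entries |
|---|---|
| All participants, or no subgroup named | 6 |
| Baseline bulbar dysfunction only | 7 |
| Baseline ALSFRS-R ≥36 | 2 |
| Slow progressors by delta-FRS | 1 |
| Not on Nuedexta | 4 |
| Not on Nuedexta, with bulbar dysfunction | 2 |
| On Nuedexta | 1 |
| Both halves of an NfL median split | 1 |
| Total | 24 |

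Subgroup-based: 7+2+1+4+2+1+1 = 18, which is 18/24 = 75%. The NfL split names both halves, so 17 entries (71%) are single-stratum.

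**Interaction terms.** Every interaction in sections 6.5.2, 6.5.3 and 6.5.9 is treatment or a covariate by visit, month or spline. The logistic model in 6.5.5 has main effects only and omits Nuedexta. The Cox model in 6.5.4 has Nuedexta as a main effect.

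**The plan's own figure.** Section 6.5.1 states 5% overall error for the primary plus the five hierarchical endpoints. With the primary passed and all five nulls true, an error requires the first test to reject, so the rate is 0.05 (simulation of 1,000,000 runs: 0.0502). The primary's own error rate is in Appendix 1 to the Master Protocol, which was not supplied. The 24 endpoints lie outside this sequence, so the 5% is not affected by them.

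**Same true effect in both strata.** Let d be the overall noncentrality and f the share of information in the smaller stratum. At two-sided 5% with 70% overall power (assumed), d = 1.960 + 0.524 = 2.484. Power is Φ(d√(1−f) − 1.960) in the larger stratum (B) and Φ(d√f − 1.960) in the smaller (S). Exactly one is significant with probability B(1−S) + S(1−B).

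| f (assumed) | B | S | Larger only: B(1−S) | Exactly one |
|---|---|---|---|---|
| 0.20 | 0.603 | 0.198 | 0.484 | 0.562 |
| 0.30 | 0.547 | 0.275 | 0.397 | 0.521 |
| 0.50 | 0.419 | 0.419 | 0.244 | 0.487 |

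That is the 49–56% range. At 80% overall power and shares of 10%, 20%, 30% and 50%, the result is 68%, 61%, 55% and 50%. An interaction test would wrongly report a difference in a nominal 5% of such trials.

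**No effect in either stratum.** Exactly one of two complementary strata is significant with probability 2 × 0.05 × 0.95 = 9.5%.

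**What the interaction test can detect.** If the strata differ by as much as the overall effect, its noncentrality is d√(f(1−f)). At 80% overall power, this gives power of 13% for a 10:90 split and 29% for 50:50.

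The documents do not give the Nuedexta share, the number of shared placebo participants, or overall power for these endpoints. The figures for f and power above are assumptions.

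**The case against.** The strongest reply is that the list is labelled as unadjusted and non-hierarchical, and that section 6.5.1 declares significance only within the five-step sequence after a positive primary. No rule turns any of these 24 endpoints into a formal claim. That stands, and it answers the multiplicity question. It does not answer the separate point that a within-stratum p-value says nothing about effect modification.

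Other parts of the reply also stand:

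- A reader might infer that each test is run at a full 5%. No threshold is written for this list; two-tailed p<0.05 is stated only for the hierarchical endpoints. The 5% used above is a reading based on nominal p-values and 95% bounds.
- A reader might infer that the trial has no subgroup comparison at all. Section 6.5.12 only adds to the Master SAP, which was not supplied and may name interaction tests.
- Bulbar dysfunction is a pre-specified target population: it is the first secondary hypothesis in Protocol section 9.4 and the population of hierarchical endpoints 1 and 3. Asking whether the drug works there needs no interaction test. A complement for time to bulbar decline is planned in SAP sections 4.2 and 6.5.4.
- The early disease state in section 6.5.12 is analysed against its complement. Its definition differs from the cut-off of 36, so it does not supply the missing stratum.
- The 49–56% figure applies only where both strata are tested. Among the single-stratum entries of this list, that is the Nuedexta pair for ALSFRS-R slope.

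One might also go further and ask for the whole list to be relabelled exploratory. The documents do not require that; since the list is already outside error control, it is a matter of preference.

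**Conclusion.** The point holds as a matter of interpretation. The R-SAP plans 18 subgroup-based endpoints out of 24, 17 of them single-stratum, and names no treatment-by-subgroup term for them. It is clearest for Nuedexta, delta-FRS class and the ALSFRS-R cut-off of 36.

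With a uniform effect, a result in one stratum and not the other is about as likely as not under the stated assumptions. Such a pattern is therefore not evidence that the effect depends on the subgroup. The counts and the absence of an interaction term rest on the R-SAP text alone; the percentages rest on assumed power and stratum shares.

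The stronger reading, that the plan breaks its own 5% error control, is not supported, because these endpoints are openly placed outside it. This is an inexpensive improvement to the analysis and its reporting.

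**What to change.** For Nuedexta use, delta-FRS class and baseline ALSFRS-R of 36 or more, replace the isolated stratum fits with one FAS model per endpoint:

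- Random-slopes endpoints: add treatment × subgroup × month with its lower-order terms. This also avoids fitting the section 6.5.3 model inside a Nuedexta stratum, where the Nuedexta covariate is constant.
- Responder endpoints: add treatment × subgroup to the logistic model, with a main effect for Nuedexta where it is the subgroup.
- Time-to-event endpoints: add treatment × subgroup to a Cox model, since a log-rank test gives no interaction estimate.

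Report both strata side by side with confidence intervals, plus the interaction estimate and p-value. State that a within-stratum p-value alone will not support a claim that the effect differs by subgroup. Do the same for bulbar dysfunction only if a bulbar-specific effect is to be claimed. If the Master SAP already provides this, a cross-reference is enough.

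Before coding delta-FRS class, reconcile its sign: section 5.1 defines it as a non-negative quantity, while the cut-offs in sections 4.1 and 4.2 are at −0.75.

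The cost is SAP wording and a few model terms on data already collected. The downside is the low power of interaction tests: subgroup statements become more cautious, and a non-significant interaction will not show that the effects are equal.

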4.2 Exploratory Endpoints

The following categories of exploratory endpoints will be evaluated:

- Rate of change in ALSFRS-R bulbar domain (Q1-Q3) score from baseline through Week 24 among participants in FAS,

- Rate of change in ALSFRS-R bulbar domain (Q1-Q3) score from baseline through Week 24 among participants in FAS with bulbar dysfunction at baseline defined as an ALSFRS-R bulbar domain (Q1-Q3) score of less than 12,
- Proportion of participants experiencing no worsening in the ALSFRS-R bulbar domain (Q1-Q3) score from baseline through Week 24 among all participants in FAS with delta-FRS less than -0.75 points/month (fast progressors),
- Rate of change in ALSFRS-R bulbar domain (Q1-Q3) score from baseline through Week 24 among all participants in FAS with delta-FRS greater than -0.75 points/month (slow progressors),
- Time to first decline of 1 or more points post baseline in the ALSFRS-R bulbar domain (Q1-Q3) score among participants in FAS with no bulbar dysfunction at baseline defined as an ALSFRS-R bulbar domain (Q1-Q3) score of 12,
- Change in other ALSFRS-R domain scores (fine motor, gross motor, respiratory, and fine and gross motor combined),
- Change in strength: HHD global percentage, HHD0, and HHD0²,
- Change in quantitative voice characteristics as measured by Aural Analytics: maximum phonation time, pause rate, breathy vocal quality, pitch instability, regulation of voicing, articulatory precision, speaking rate, articulation rate, and monotonicity,
- Change in biofluid biomarkers of neurodegeneration and neuromuscular degeneration: serum creatinine, and serum and cerebrospinal fluid (CSF) neurofilament light chain (NfL),
- Change in patient-reported outcomes: ALSAQ-40 physical mobility, independence in activities of daily living, eating and drinking, communications, and emotional reactions domain scores and ALSAQ-40 symptom index, CNS-BFS total score, and CNS Lability Scale (CNS-LS),
- Change in plasma concentration of pridopidine and its metabolites,
- Change in respiratory function as assessed by home spirometry, and
- Time to clinical events: first hospitalization due to a serious adverse event (SAE), first hospitalization due to an ALS-related SAE, first use of assisted ventilation, first placement of a feeding tube, first time reaching King's stage 4a or 4b, and first instance of any of the following events: hospitalization for an SAE, feeding tube placement, tracheostomy, initiation of permanent assisted ventilation (PAV), or death.

Safety Endpoints

In addition to the safety endpoints described in the M-SAP, the following RGD regimen-specific safety endpoint will be evaluated:

- QT prolongation: Proportion of participants meeting ECG stopping rules or meeting ECG monitoring rules 1, 2, or 3 times.

5. Measurement Definitions

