2 STUDY OBJECTIVES AND ENDPOINTS

Primary Efficacy Objective:

- To evaluate the efficacy of pridopidine as compared to placebo on ALS disease progression.

Secondary Efficacy Objective:

- To evaluate the effect of pridopidine on selected secondary measures of disease progression, including survival.

Safety Objective:

- To evaluate the safety of pridopidine in ALS patients.

Exploratory Efficacy Objective:

- To evaluate the effect of pridopidine on selected biomarkers and endpoints.

Primary Efficacy Endpoint:

Change in disease severity as measured by the ALS Functional Rating Scale-Revised (ALSFRS-R) total score using a Bayesian repeated measures model that accounts for loss to follow-up due to mortality.

Secondary Efficacy Endpoints:

- Change in bulbar function as measured by the ALSFRS-R bulbar subdomain (Q1-Q3) score among participants with bulbar dysfunction at baseline.
- Change in bulbar function as measured by the ALSFRS-R bulbar subdomain (Q1-Q3) score among all randomized participants.
- Change in speech as measured by the ALSFRS-R speech domain score (Q1) among all randomized participants.
- Change in respiratory function as measured by slow vital capacity (SVC).
- Change in bulbar function as measured by the ALSFRS-R bulbar subdomain (Q1-Q3) score among participants with rapid pre-baseline progression.
- Time to first evidence of bulbar dysfunction.
- Change in muscle strength as measured isometrically using hand-held dynamometry (HHD) and grip strength.
- Survival.

Safety Endpoints:

- Treatment-emergent adverse and serious adverse events.
- Changes in laboratory values and treatment-emergent and clinically significant laboratory abnormalities.
- Changes in ECG parameters and treatment-emergent and clinically significant ECG abnormalities.
- Treatment-emergent suicidal ideation and suicidal behavior.

Exploratory Efficacy Endpoints:

HEALEY ALS Platform Trial
Regimen-Specific Appendix D, Pridopidine
Version 2.0, 15-July-2021
CONFIDENTIAL

- Changes in quantitative voice characteristics.
- Changes in biofluid biomarkers of neurodegeneration.
- Changes in patient reported outcomes (e.g. CNS-BFS, CNS-LS).
- Change in respiratory function as assessed by home spirometry.

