9.4 Secondary Efficacy Endpoints

If the primary analysis demonstrates significant slowing of decline in ALSFRS-R among participants randomized to pridopidine, then the following secondary hypotheses will be tested in the specified sequence with overall type I error rate controlled using a sequential closed-testing procedure:

1. Rate of change in ALSFRS-R bulbar subdomain (Q1-Q3) score among participants with bulbar dysfunction at baseline,
2. Rate of change in ALSFRS-R bulbar subdomain (Q1-Q3) score among all randomized participants,
3. Rate of change in the speech sub-score of the ALSFRS-R (Q1) among all randomized participants
4. Rate of change in SVC maximum percent of predicted among all randomized participants,
5. Rate of change in ALSFRS-R bulbar subdomain (Q1-Q3) score among participants with pre-baseline slope ≥ 0.75 points/month,
6. Time to onset of bulbar symptoms among participants free of bulbar dysfunction at baseline,
7. Rate of change in HHD percent change from baseline among all randomized participants,
8. Time to death or death equivalent

Analyses for each secondary hypothesis will use an ITT analysis sample that includes placebo participants from concurrently enrolling regimens. Analyses of ALSFRS-R bulbar subdomain,

CNS-BFS, HHD, and SVC will use shared-baseline linear mixed models that adjust for time since onset of weakness, pre-baseline slope, baseline riluzole use, baseline edaravone use, baseline Nuedexta use, and site of onset and their interactions with time since baseline, and include random intercepts and slopes by regimen and by participant with unstructured covariance at each level. Given low expected event rates, time to bulbar onset and time to death or death equivalent will use log-rank tests. Per protocol analyses will also be performed to evaluate the effects of pridopidine on participants complying with study regimen. Details of endpoint measures, analysis samples, statistical models, and the closed-testing procedure will be described in the regimen-specific statistical analysis plan.

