5.1 ALSFRS-R

The definitions of ALSFRS-R scores are the same as described in the M-SAP with the clarification that scores will be considered missing in cases of item nonresponse. Pre-baseline slope in ALSFRS-R (delta-FRS) is defined as 48 minus the baseline ALSFRS-R total score then divided by the number of months from onset of symptomatic weakness to the Baseline Visit. The number of months will be calculated as the difference in days from onset of symptomatic weakness to the Baseline Visit multiplied by 12 / 365.25. The date of onset of symptomatic weakness will be imputed as the fifteenth day of a month if not specified more precisely.

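### The delta-FRS cut-offs in SAP 4.2 have the opposite sign to the definition in SAP 5.1, so as written the fast-progressor set is empty and the slow-progressor set is everyone

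*SAP*

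**What the plan says.** SAP 5.1 gives the definition: "Pre-baseline slope in ALSFRS-R (delta-FRS) is defined as 48 minus the baseline ALSFRS-R total score then divided by the number of months". The interval counted begins with the first symptomatic weakness and ends at baseline. Months are the day count multiplied by 12/365.25.

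Three endpoints then use a cut-off on this quantity:

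- SAP 4.2, proportion with no worsening in the bulbar score: "among all participants in FAS with delta-FRS less than -0.75 points/month (fast progressors").
- SAP 4.2, rate of change in the bulbar score: "among all participants in FAS with delta-FRS greater than -0.75 points/month (slow progressors").
- SAP 4.1, proportion with no worsening in the bulbar score: "among all participants in FAS with delta-FRS slower than -0.75 points/month (slow progressors"). This item stands under "Other Secondary Efficacy Endpoints (pre-specified non multiplicity adjusted non-hierarchical").

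The first exploratory endpoint in SAP 4.2 is the unrestricted version of the slow-progressor item: "Rate of change in ALSFRS-R bulbar domain (Q1-Q3) score from baseline through Week 24 among participants in FAS".

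The protocol uses the positive convention. Section 9.4 refers to "participants with pre-baseline slope ≥ 0.75 points/month", and section 2 describes the same endpoint as being "among participants with rapid pre-baseline progression".

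**The concern.** The definition and the cut-offs use opposite sign conventions. Section 5.1 measures points lost per month, so decline is positive. Section 4.2 treats the slope as a negative number, so that fast decline lies below a negative threshold. Both cannot hold in one program.

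The two exploratory items fail in different ways if the stated inequalities are coded. The fast-progressor analysis has no participants, which would probably be noticed. The slow-progressor analysis runs without complaint on essentially the whole FAS and returns the unrestricted result under a subgroup title. SAP 7.2 gives exploratory efficacy endpoints as an example of supplementary results, which are validated only by inspecting log files. A filter that keeps everyone need not produce an error or warning.

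The fast item is also the only endpoint listed in SAP 4.1 and 4.2 for fast progressors defined by delta-FRS. The protocol had placed bulbar decline in rapid progressors fifth in its testing sequence. What the SAP retains for that population is the item that comes out empty.

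**Working it through.** **Inputs**

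- delta-FRS = (48 − S) / M, where S is the baseline total and M is months since onset (SAP 5.1).
- M = days × 12/365.25 (SAP 5.1).
- S runs from 0 to 48 (the imputation limits in SAP 6.5.10).
- Fast: delta-FRS < −0.75. Slow: delta-FRS > −0.75 (SAP 4.2).
- Rapid in the protocol: pre-baseline slope ≥ 0.75 (Protocol 9.4).

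**Step 1: sign.** Since S ≤ 48, the numerator is at least 0. With onset before baseline, M > 0. Hence delta-FRS ≥ 0, which is always above −0.75. The literal fast rule can never be met and the literal slow rule always is.

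**Step 2: examples.**

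| Baseline S | Months | delta-FRS | Literal 4.2 rule | Meant, by label |
|---|---|---|---|---|
| 36 | 12 | 12/12 = 1.00 | slow | fast |
| 42 | 12 | 6/12 = 0.50 | slow | slow |
| 36 | 24 | 12/24 = 0.50 | slow | slow |
| 30 | 36 | 18/36 = 0.50 | slow | slow |

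**Step 3: exhaustive check.** All 49 scores were crossed with every onset-to-baseline interval in an assumed range. These counts test the rule; they do not estimate patient proportions.

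| Interval (days) | Combinations | < −0.75 | > −0.75 |
|---|---|---|---|
| 1 to 1,096 | 49 × 1,096 = 53,704 | 0 | 53,704 |
| 1 to 3,650 | 49 × 3,650 = 178,850 | 0 | 178,850 |

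The minimum value is 0 in both ranges.

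**Step 4: with the sign aligned.** Using +0.75 on the longer range, 47,700 combinations are fast, 131,146 are slow and 4 lie exactly on the cut-off (47,700 + 131,146 + 4 = 178,850). The rule then separates two non-empty groups. The four ties are S = 36, 24, 12 and 0 at 487, 974, 1,461 and 1,948 days. For example, 487 × 12/365.25 = 16 months and 12/16 = 0.75. The strict inequalities in 4.2 place such a value in neither group.

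**Step 5: could a negative value arise?** Only if the onset date falls after baseline. SAP 5.1 imputes the 15th when the day of onset is unknown. An onset imputed to the 15th with baseline on the 10th of the same month gives M = −5 × 12/365.25 = −0.164, so S = 36 would give 12/(−0.164) ≈ −73. That is a date artefact, not a fast progressor in the intended sense.

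**Step 6: does another provision reverse the sign?** None in the supplied documents does. The master SAP was not supplied, but SAP section 1 makes this regimen-specific SAP authoritative over it. The same section ranks this SAP above the protocol appendix on secondary and exploratory analyses, so the positive cut-off in Protocol 9.4 shows intent but does not override 4.2.

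**The case against.** The strongest reply is that nobody could mistake the intent. Each item is labelled fast or slow, the size of the threshold is fixed at 0.75, and the protocol gives the same size with a positive sign. Only one split fits, so little analytic freedom is left open, and the endpoints affected cannot support a confirmatory claim. That stands, and it limits the point to a correction that should be made; nothing in the trial's main inference depends on it. It does not remove the error, because the rule as written still selects the wrong population, and in the slow-progressor analysis it does so silently.

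The SAP 4.1 item is worded by speed and can be read as intended. That is fair, and it is not counted as wrong. It belongs in the correction because it carries the same negative number. If it were coded as greater than −0.75, it would repeat the second hierarchical endpoint, which uses the same responder definition in the whole FAS.

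SAP 7.2 says that analyses failing through small sample size or non-convergence will be omitted with comment. It does not mention a group emptied by a mis-signed cut-off. The fast analysis could be dropped under that clause, but this is not certain.

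The grid counts add nothing to the one-line proof in Step 1 beyond confirmation, and ties at 0.75 are rare. Both remarks are correct. The date artefact in Step 5 is a separate matter that correcting the sign does not solve.

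**Conclusion.** The point holds. Under SAP 5.1 the two cut-offs in SAP 4.2 cannot separate fast from slow progressors: the fast set is empty, and the slow set is every FAS participant with a computable delta-FRS. Two exploratory endpoints give the wrong subgroup if coded as written, and one non-multiplicity-adjusted secondary endpoint in SAP 4.1 is ambiguous. The Bayesian primary analysis, the five hierarchical secondary endpoints and the models that adjust linearly for delta-FRS are unaffected.

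The conclusion assumes only that recorded or imputed onset precedes baseline and that the total lies between 0 and 48. The rule is inconsistent, not undefined, since labels and protocol agree on the intended split. An analyst who found the empty group would probably reverse the sign, but that correction would then be made during analysis when it belongs in the plan.

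**What to change.** In SAP 4.1 and 4.2, state the groups on the 5.1 scale: fast progressors have delta-FRS ≥ 0.75 points/month and slow progressors have delta-FRS < 0.75 points/month. This agrees with Protocol 9.4 and assigns the boundary value to one group. The equivalent alternative is to define delta-FRS in 5.1 as baseline total minus 48, divided by months, and to use ≤ −0.75 for fast and > −0.75 for slow throughout; the split is identical.

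The cost is three lines of wording, or one line in 5.1 plus matching inequalities. It needs no new data or analyses. Record the correction before unblinding. If that point has passed, document which rule was actually programmed.
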